3.4 OUTCOME(S) OF INTEREST

Digitalis intoxication and rhabdomyolysis /myopathy will be analyzed separately as the outcomes of interest. Digitalis intoxication will be defined as patients with ICD-9 codes 972.1 and/or E942.1 that have been used in published studies³⁻⁵. Given that these codes have not been validated, a secondary analysis will be performed among the patients who had a claim of the above ICD-9 codes plus at least one laboratory testing claim and/or hospitalization within 30 days.

Rhabdomyolysis and myopathy will be defined by an algorithm based on the ICD-9 codes, lab testing, and/or hospitalization that have been validated in a published study⁶. Specifically, the patients who meet one of the following four criteria based on the ICD-9 codes, lab testing/Current Procedure Terms (CPT) codes, and/or hospitalization will be identified and defined as cases:

- 1) any code of myoglobinuria (ICD-9 code 791.3) or rhabdomyolysis (ICD-9 code 728.88);
- 2) a primary code of "other disorders of muscle" (ICD-9 code 728.89);
- 3) a secondary code of "other disorders of muscle (ICD-9 code 728.89) plus any serum creatine kinase (CK) test (CPT codes: 82550, 82552, 82553, 82554, 80012, 80016, 80018, 80019) within 7 days of hospitalization/admission for the ICD-9 code 728.89;
- 4) a secondary code of "other disorders of muscle (ICD-9 code 728.89) plus hospital discharge code for acute renal failure (ICD-9 code 584.x).

3.5 COVARIATE(S)

The following covariates will be adjusted for in the multivariate analyses: age at baseline, gender, cohort entry date, duration of AF/AFL, congestive heart failure (CHF) history, diabetes history, hypertension history, stroke history, myocardial infarction history, and dose of digoxin (or statins). The major medications that are known to have potent interactions with statins or digoxin will additionally be adjusted for as potential confounders. For digitalis intoxication, the medications will be those with potent interactions, including arbutamine, atazanavir, calcium chloride, calcium gluceptate, calcium gluconate, and saquinavir. The drugs with interaction that are generally considered to be moderate (e.g. aspirin) or mild (e.g. acetaminophen) will not be considered⁷. For the outcome of rhabdomyolysis and myopathy, the major medications will include erythromycin, clarithromycin, azithromycin, fusidic acid, warfarin, dicoumarol, nefazodone, ketoconazole, itraconazole, cholestyramine, mibefradil, digoxin, gemfibrozil, cyclosporine, chlorzoxazone, and vitamins niacin⁸. History of renal failure (except for acute renal failure) will also be adjusted for the outcome of rhabdomyolysis and myopathy.

The history of the medical conditions will be defined as a diagnosis in the baseline period based on the ICD-9 codes (codes to be provided). The count of the number of diagnoses of AF/AFL in the baseline period will be used as a surrogate for the duration of AF/AFL since the accurate information is not available in the LabRx database. All medications will be identified using the National Drug Code (NDC) directory. Maintained by the Food and Drug Administration (FDA), NDC is a code-set that serves as a universal product identifier for human drugs and biologics. The directory consists of prescription and a few selected over-the-counter drugs that are in commercial distribution in the United States. The products have been listed in accordance with the Drug

Listing Act and applicable Code of Federal Regulations for submitting drug product information to the FDA (see: <http://www.fda.gov/cder/ndc/>).

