3.3 EXPOSURE MEASUREMENT

Exposure will be defined as on-drug treatment or off-drug treatment. To identify exposure, all prescriptions for digoxin (or statins), dronedarone, and amiodarone will be identified and treatment episodes calculated. Statins of interest include atorvastatin, simvastatin, lovastatin, and pravastatin. Fluvastatin and rosuvastatin will not be considered for the potential interaction with dronedarone because they are not metabolized or only weakly metabolized by CYP3A4 and are not P-gp substrates.

Exposure will be categorized into the following three groups: 1) concomitant use of digoxin (or statins) and dronedarone, 2) concomitant use of digoxin (or statins) and amiodarone, and 3) digoxin (or statins) alone as the reference group, i.e. digoxin (or statins) without concomitant use of either dronedarone or amiodarone. The concomitant use of digoxin (or statins) and dronedarone (or amiodarone) will be defined as the treatment period during which a patient is on both of the drugs. Digoxin (or statins) alone will be defined as the treatment period during which a patient is on digoxin (or statins), but not on dronedarone or amiodarone. Amiodarone is included as part of exposure of interest because it is one of the major drugs that are identified to have potent interactions with digoxin (or statins) as a multi-channel blocker displaying antiarrhythmic properties of all four Vaughan-William's classes.

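### The digitalis intoxication model picks co-medication confounders by an interaction-severity label and bars moderate interactors, so common co-treatments that affect digoxin may stay unadjusted and bias the hazard ratio in either direction

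*Protocol*

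**What the plan says.** Protocol section 3.5 gives the purpose of the drug covariates: "The major medications that are known to have potent interactions with statins or digoxin will additionally be adjusted for as potential confounders". The drugs chosen for the digitalis outcome are the potent interactors, "including arbutamine, atazanavir, calcium chloride, calcium gluceptate, calcium gluconate, and saquinavir". The next sentence closes the door on the rest: "The drugs with interaction that are generally considered to be moderate (e.g. aspirin) or mild (e.g. acetaminophen) will not be considered". The source cited for this grading is a drug-interaction website (reference 7).

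The same section says how drugs are found: "All medications will be identified using the National Drug Code (NDC) directory". It also lists the other covariates for this outcome: age, gender, cohort entry date, a surrogate for AF/AFL duration, history of heart failure, diabetes, hypertension, stroke and myocardial infarction, and digoxin dose.

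Section 3.3 defines the reference group as "digoxin (or statins) without concomitant use of either dronedarone or amiodarone". It treats amiodarone as an exposure group of its own: "Amiodarone is included as part of exposure of interest because it is one of the major drugs that are identified to have potent interactions".

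**The concern.** A confounder is a variable related to both the exposure and the outcome. A severity grade speaks to only one side of that, the strength of the pairwise interaction with digoxin. It says nothing about how common a drug is in AF patients or whether its use differs between the exposure groups. A moderate interaction in a widely used drug can confound far more than a potent one in a drug almost nobody takes.

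The six named drugs are a diagnostic agent, three calcium salts and two HIV protease inhibitors. They are plausibly rare among the prescription claims of AF patients, although the protocol gives no frequencies. In the same paragraph the statin model names macrolides, azoles and cyclosporine; the digoxin list names none of these.

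At stake is a safety estimate meant to exclude hazard ratios of 1.42 to 1.59 for digitalis intoxication (section 3.6, Table 3). A modest confounding bias is of the same order as that margin.

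**Working it through.** **1. The plan's own figures.** Inputs from section 3.6 and Table 3: 44,000 digoxin patients at five years, baseline rate 1.1%, dronedarone prevalence 17.1%, two-sided alpha 0.05, power 80%, 30% right censoring. I assume that the censoring is spread evenly over follow-up and so costs 15% of events.

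- Events = 44,000 × 0.011 × (0.829 + 0.171 × 1.42) × 0.85 = 441.
- Detectable HR (Schoenfeld) = exp[(1.960 + 0.842) / √(0.171 × 0.829 × 441)] = 1.425, against the stated 1.42. Power at 1.42 is 0.79.
- Events for HR 1.5 = (1.960 + 0.842)² / [0.171 × 0.829 × (ln 1.5)²] = 337, against 336 in section 5.

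The power figures are sound. They set the scale against which bias should be judged.

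**2. Bias from one omitted co-medication.** Bias factor B = [1 + p1(R − 1)] / [1 + p0(R − 1)], where p1 is the prevalence of the co-medication in dronedarone-plus-digoxin time, p0 its prevalence in digoxin-alone time, and R its hazard ratio for toxicity. The protocol gives none of the three, so all values below are assumptions. Power uses the 441 events above.

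| R | p1 | p0 | B | True 1.42 appears as | Power at true 1.42 |
|---|---|---|---|---|---|
| any | equal | equal | 1.00 | 1.42 | 0.79 |
| 1.5 | 15% | 25% | 1.075/1.125 = 0.96 | 1.36 | 0.68 |
| 2 | 20% | 30% | 1.20/1.30 = 0.92 | 1.31 | 0.57 |
| 2 | 10% | 30% | 1.10/1.30 = 0.85 | 1.20 | 0.31 |
| 2 | 10% | 35% | 1.10/1.35 = 0.81 | 1.16 | 0.21 |

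With the last imbalance reversed (35% against 10%), B = 1.35/1.10 = 1.23, so a true hazard ratio of 1.0 would appear as 1.23. With 44,000 × 0.011 × 0.85 = 411 events under the null, the two-sided test would then reject about 35% of the time instead of 5%. At R = 1.5 and a 10-point imbalance either way, it would reject about 6% of the time.

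**3. What the listed drugs can contribute.** Suppose one of them is used by 0.1% to 0.5% of patients (44 to 220 of 44,000; assumed). Even with R = 3 and all use in one group, the factor is at most 1 + 0.005 × 2 = 1.01. Adjusting for a drug that rare moves the hazard ratio by about 1% at most.

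**4. Whether anything else in the protocol closes the gap.** Average daily digoxin dose is quantity prescribed over days supplied (section 3.3), so it measures the dose dispensed. An interacting drug changes exposure or toxicity at a given dose. Medical history is a baseline diagnosis and only a partial proxy for treatment. No restriction, propensity score or sensitivity analysis on co-medication is stated.

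**The case against.** Several points stand.

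- The word introducing the six drugs leaves the list open to other potent interactors. The only example of a moderate drug is aspirin. Whether a given rate-control drug, macrolide or diuretic is graded potent or moderate depends on reference 7, which is not at hand. Any that is graded potent is already covered.
- Amiodarone, which the protocol calls a major interacting drug, is handled through the exposure groups. Digoxin dose, heart failure, hypertension and other history are adjusted for and may absorb part of the bias in the table.
- Interacting drugs in the reference group are not an error in themselves, since dronedarone co-users may take them too. With equal use the factor is 1.00.

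A reader might infer that the hazard ratio is certainly confounded, or that it is most likely pulled down so that a real signal is hidden. The protocol supports neither: it gives no co-medication use by group, so size and direction are both unknown. Nor does it show that the six drugs are virtually absent from the data; that is plausible but unquantified.

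What does not stand is leaving the matter to a statistical analysis plan. The bar on moderate interactors is a stated rule, and an analysis plan that restored them would contradict the protocol.

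**Conclusion.** The point holds as a weakness in a stated rule. It is not a demonstrated bias. Section 3.5 selects co-medication confounders for digitalis intoxication by potency label and shuts out moderate interactors whether or not their use is balanced. The shifts calculated above (1.42 read as 1.16 to 1.36, or 1.0 read as up to 1.23) rest wholly on an assumed confounder hazard ratio of 1.5 to 2 and an assumed imbalance of 10 to 25 points, for one omitted drug class and without credit for the existing covariates. Within that range the bias is large enough to matter to a study of this resolution. It should be fixed; confidence is moderate, because the documents do not show that the imbalance exists.

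**What to change.** - Delete the sentence in section 3.5 that bars moderate and mild interactors.
- Pre-specify adjustment for dispensed drugs that affect digoxin exposure or toxicity, whatever their potency label. As general pharmacology and not from the protocol, candidates are P-gp-inhibiting rate- or rhythm-control drugs, macrolides, azoles, cyclosporine and diuretics.
- Measure each at or just before the start of each exposure episode. Use during the episode may itself change because dronedarone was started, and adjusting for it could introduce bias.
- Add one sensitivity analysis that removes time on the main interacting antiarrhythmic or rate-control drugs from all three exposure groups.

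The cost is protocol wording and an NDC list. The prescription claims are already in the database. With about 441 events expected at five years, a few more covariates cost little precision in the main analysis; the sensitivity analysis will lose some person-time.

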1 INTRODUCTION

Dronedarone (MULTAQ[®]), like amiodarone, is a multi-channel blocker displaying antiarrhythmic properties of all four Vaughan-William's classes. Although structurally related to amiodarone, dronedarone shows different relative effects on individual ion channels, and its structure was modified with the intent to eliminate the non-cardiovascular effects of amiodarone. Dronedarone has been shown to be effective for reduction of the risk of cardiovascular hospitalization or death in patients with AF/AFL at the dose of 400 mg BID. The efficacy and safety of dronedarone have been evaluated in a comprehensive non-clinical testing program and extensive comprehensive clinical program in compliance with the International Conference on Harmonization (ICH) Good Clinical practice (GCP) guidelines.

The continuous assessment of all potential risks of dronedarone during its development has identified risk of drug-drug interactions with potent CYP3A4 inhibitors (such as ketoconazole). Dronedarone may have potential interactions with CYP3A4 substrates (such as some statins), and digitalis (such as digoxin). Although managed appropriately during clinical trials, the potential risks of these interactions need to be monitored in dronedarone users in the real life setting.

In order to further identify and evaluate dronedarone's potential interactions with frequently co-prescribed drugs, sanofi-aventis proposes epidemiologic studies using automated databases as part of the Risk Management Plan. They are done in addition to routine pharmacovigilance practices to ensure that the identified and potential risks are minimized in the real life setting, both in the US and in Europe. Using a US automatic claims database, LabRx, this epidemiologic study will be conducted once the number of dronedarone users is large enough to allow for analyses with sufficient statistical power.

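### The statin model's covariate list names neither diltiazem nor verapamil (nor thyroid or liver disease), so the dronedarone hazard ratio for rhabdomyolysis/myopathy may be left confounded, by an amount and in a direction the protocol cannot settle

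*Protocol*

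**What the plan says.** Protocol Section 3.5 has three layers of adjustment for the rhabdomyolysis/myopathy outcome.

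- A general list for both outcomes: "age at baseline, gender, cohort entry date, duration of AF/AFL, congestive heart failure (CHF) history, diabetes history, hypertension history, stroke history, myocardial infarction history", together with the dose of the index drug.
- A medication layer, chosen by a rule: "The major medications that are known to have potent interactions with statins or digoxin will additionally be adjusted for as potential confounders". For this outcome "the major medications will include erythromycin, clarithromycin, azithromycin, fusidic acid, warfarin, dicoumarol, nefazodone, ketoconazole, itraconazole, cholestyramine, mibefradil, digoxin, gemfibrozil, cyclosporine, chlorzoxazone", followed by niacin, which makes 16 agents.
- One further condition: "History of renal failure (except for acute renal failure) will also be adjusted for the outcome of rhabdomyolysis and myopathy".

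Diltiazem, verapamil, hypothyroidism and liver disease appear nowhere in the protocol.

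Three other places matter. Section 1 gives the mechanism: "Dronedarone may have potential interactions with CYP3A4 substrates (such as some statins), and digitalis (such as digoxin". Section 3.3 says "Statins of interest include atorvastatin, simvastatin, lovastatin, and pravastatin", and sets fluvastatin and rosuvastatin aside on CYP3A4 and P-gp grounds. Section 3.3 also defines the reference group as "digoxin (or statins) without concomitant use of either dronedarone or amiodarone". Section 3.7 describes a Cox model and no propensity score, matching or other means of confounding control.

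**The concern.** Section 3.5 calls the listed drugs potential confounders, but the selection rule asks only how strongly a drug interacts with the index drug. A confounder must also differ in frequency between the exposure groups. By that test, an AF drug that inhibits CYP3A4 is a stronger candidate than an antifungal or a macrolide, which are prescribed for reasons unrelated to AF. The list has several drugs of the latter kind and leaves out diltiazem and verapamil. It does contain digoxin, so an AF rate-control drug is not foreign to it.

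The same question of consistency applies to the conditions. Renal failure is added for this outcome alone, so the plan accepts adjusting for a condition that predisposes to myopathy. Hypothyroidism and liver disease are commonly placed in that class (clinical knowledge, not stated in the protocol) but are not listed.

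What is at stake is the purpose of the study. Section 3.6 presents the result as ruling out a given hazard ratio. A downward bias would make that reassurance too easy to obtain.

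**Working it through.** **1. The plan's own figure.** Section 3.6 and Table 3 give a hazard ratio of 1.61 for 86,000 statin users, with 80% power, two-sided alpha 0.05, 17.1% exposed, a 0.3% baseline rate and 30% censoring. I compared two proportions, 0.3% and 0.3% × 1.61 = 0.483%, after multiplying the cohort by 0.7:

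- total 86,000 × 0.7 = 60,200; exposed 60,200 × 0.171 = 10,294; unexposed 49,906
- power = 0.800, so the stated figure reproduces.

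Expected events at the baseline rate: 86,000 × 0.003 × 0.7 = 180.6, about 181. None of these figures depends on the covariate list.

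**2. Bias from one omitted binary factor.** With prevalence p1 in statin-plus-dronedarone time, p0 in statin-alone time and risk ratio RR for the outcome,

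bias factor = (1 + p1(RR − 1)) / (1 + p0(RR − 1)).

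The protocol gives none of these inputs; all values below are assumptions.

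Diltiazem or verapamil, p1 = 10%, p0 = 25%:

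| RR | Factor | True 1.50 reads | True 1.61 reads |
|---|---|---|---|
| 1.5 | 1.05/1.125 = 0.93 | 1.40 | 1.50 |
| 2 | 1.10/1.25 = 0.88 | 1.32 | 1.42 |
| 3 | 1.20/1.50 = 0.80 | 1.20 | 1.29 |

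Putting the last column into the step 1 calculation, power at a true hazard ratio of 1.61 falls from 80% to about 66%, 53% and 31%.

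**3. Sensitivity to the assumed direction.** With the prevalences reversed (25% under co-use, 10% alone), the factors are 1.125/1.05 = 1.07, 1.25/1.10 = 1.14 and 1.50/1.20 = 1.25. With equal prevalences the factor is 1.00 whatever the RR.

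**4. Hypothyroidism, as an illustration.** If p1 = 20% and p0 = 10%, RR 1.5, 2 and 3 give 1.10/1.05 = 1.05, 1.20/1.10 = 1.09 and 1.40/1.20 = 1.17. Nothing in the protocol supports the higher prevalence under co-use, so the sign is also an assumption. Liver disease would behave in the same way, with equally unknown inputs.

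**5. Both together at the middle values.** 0.88 × 1.09 = 0.96, so a true 1.50 reads about 1.44. For scale, the standard error of the log hazard ratio with 181 events is about 1/√(181 × 0.171 × 0.829) = 0.20. That puts the 95% limits a factor of about 1.47 either side of the estimate.

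**The case against.** The strongest objection is that confounding has not been shown. It needs the omitted factors to raise myopathy risk and to differ in prevalence between statin-plus-dronedarone and statin-alone time. The protocol states neither, and every prevalence and risk ratio above is assumed. This stands. It limits the point to possible bias of unknown size and sign.

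A reader might infer that the list is closed. For the drugs the text does not say so: they follow a potency rule and are introduced in wording that does not claim completeness, and an analysis plan that is not shown may extend them. The conditions are stated more firmly. Even so, an analyst who follows Section 3.5 as written would not be led to add diltiazem or verapamil.

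A reader might also infer that thyroid or liver disease must push the hazard ratio up, because Section 1 says of dronedarone that "its structure was modified with the intent to eliminate the non-cardiovascular effects of amiodarone", so that such patients would be steered towards it. That sentence mentions neither thyroid nor liver. At most it bears on the choice between dronedarone and amiodarone, whereas the planned reference is statin use without either drug. It does not show that these conditions are commoner under dronedarone than under statin alone.

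Nor does the protocol say that rate-control patients fill the reference group, which may include patients on other antiarrhythmics or on none. Adjustment for digoxin, heart failure, hypertension and the AF-duration surrogate captures some differences in AF management. It does not identify who is taking diltiazem or verapamil.

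Finally, at the middle assumed values the two biases nearly cancel (0.96), a shift that is small beside the sampling error. That is fair, but the cancellation depends on the assumed directions and cannot be relied on.

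**Conclusion.** The point holds in a limited form. Section 3.5 selects the drug covariates for rhabdomyolysis/myopathy by interaction potency and names neither diltiazem nor verapamil, although the protocol gives CYP3A4 as the statin interaction pathway and describes no other confounding control. If these drugs are commoner in statin-alone time, the dronedarone hazard ratio may be biased downward, by a factor of 0.93 to 0.80 under the assumed 10% versus 25% and RR 1.5 to 3. This rests on general pharmacology and on assumed inputs; the true size and direction are unknown.

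The absence of hypothyroidism and liver disease is a weaker, secondary part. It is inconsistent with adding renal failure, but the direction of any bias against the statin-alone reference is not established. The stronger statement, that the hazard ratio is confounded by factors known to drive the choice of dronedarone, is not supported by the document. No sample-size figure in the protocol changes.

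**What to change.** In Section 3.5, for the rhabdomyolysis/myopathy model:

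- add current diltiazem or verapamil use as a time-varying covariate, defined by days supplied;
- add baseline history of hypothyroidism and of liver disease, at least in a sensitivity analysis;
- report the dronedarone hazard ratio with and without these terms, and tabulate the prevalence of each factor by exposure group, so that the size and direction of any confounding can be seen.

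If the sponsor prefers to leave any of them out, the protocol should give the reason.

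The cost is a sentence or two and the code lists. Diagnoses and dispensings come from the claims and drug codes that the study already uses. The downside is about three more parameters with some 181 expected events. If that strains the model, listed drugs that turn out to be rarely dispensed could be pooled into one indicator; the protocol does not say how often each is used, so that has to be checked in the data first.

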Rhabdomyolysis and myopathy will be defined by an algorithm based on the ICD-9 codes, lab testing, and/or hospitalization that have been validated in a published study.

Covariates: Covariates in the multivariate analyses will include age at baseline, gender, cohort entry date, duration of AF/AFL, congestive heart failure (CHF), diabetes, hypertension, stroke, myocardial infarction, and dose of digoxin (or statins). The major medications that are known to have potent interactions with digoxin or statins will additionally be adjusted as potential confounders, while for rhabdomyolysis and myopathy, chronic renal failure will also be adjusted for.

Statistical analysis: Descriptive statistical analysis will be conducted to characterize the study participants. Cox proportional hazards regression modeling will be used to provide estimates of the relative hazard of the outcome of interest associated with concomitant use of digoxin (statins) and dronedarone, concomitant use of digoxin (or statins) and amiodarone, using digoxin (statins) alone as the reference group. Dose-response relationship with cumulative dose and treatment duration will be estimated if a positive association is observed.

Timelines: The interim study reports will be submitted annually in December, 2010 to 2014. The final study report will be submitted in December 2016 at the latest. The study observation period will be from July 20, 2009 (the launch date of dronedarone in the US to the latest date of available data by August 31 of each year in the yearly study report).

TABLE OF CONTENTS

LIST OF TABLES	6
LIST OF FIGURES	6
ABBREVIATIONS	7
1 INTRODUCTION	8
2 STUDY OBJECTIVE(S)	8
3 METHODS	8
3.1 STUDY DESIGN	8
3.1.1 Source population(s)/database(s) used	9
3.2 STUDY POPULATION.....	9
3.3 EXPOSURE MEASUREMENT	9
3.4 OUTCOME(S) OF INTEREST	11
3.5 COVARIATE(S).....	11
3.6 SAMPLE SIZE.....	12
3.7 STATISTICAL ANALYSIS.....	12
4 CONFIDENTIALITY AND ETHICAL CONSIDERATIONS	12
5 STUDY TIMELINES	12
6 REFERENCES	13
7 TABLES AND FIGURES	14
8 APPENDICES	17

LIST OF TABLES

Table 1 Distribution of gender, age, and region of patients in the LabRx as of 2008 and in the US general population in 2005	14
Table 2 Age distribution in AF/AFL Patients in the LabRx (1/1985-3/2008).....	15
Table 3 Estimated sample size	16

LIST OF FIGURES

N/A

ABBREVIATIONS

AF	Atrial fibrillation
AFL	Atrial flutter
CHF	Congestive heart failure
CPT	Current Procedural Terminology
GCP	Good Clinical Practice

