2 STUDY OBJECTIVE(S)

The goal of this study is to provide safety information about dronedarone use in the US. The objectives of this study are to evaluate the possibility of dronedarone increasing the dose-related adverse events of the following concomitantly used drugs: digoxin (digitalis intoxication) and statins (rhabdomyolysis and myopathy).

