3 METHODS

3.1 STUDY DESIGN

A retrospective cohort study is designed using information from a US claims database which will allow more facile implementation and explanation of the results among cohort of digoxin (statins) users and digoxin (statins) plus dronedarone users than a case-control study.

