The treatment duration or follow-up time on digoxin (or statins) alone will begin accumulating on the first day of digoxin (or statins) prescription and continue with the subsequent continuous digoxin (or statins) prescriptions until: 1) a prescription for dronedarone (or amiodarone) overlapping the digoxin (or statins) days supplied, or 2) the end of the digoxin (or statins) days supplied (in addition to a grace period of up to 30 days, to account for non-adherence), 3) the occurrence of the outcome, 4) the enrollment end of membership, 5) the end of the observation period, whichever comes first. The follow-up time of the concomitant use of digoxin (or statins) and dronedarone (or amiodarone) will be defined using the same methodology as described above. It will however begin on the first day of overlapping days supplied for digoxin (or statins) and dronedarone (or amiodarone) and will finish with the end of overlap of the days supplied for digoxin (or statins) and dronedarone (or amiodarone) (in addition to a grace period of up to 30 days) or the other endpoints, whichever comes first. Prescriptions will be treated as continuous if they are not interrupted by a break of greater than 30 days. If a gap of greater than 30 days occurred, patients may still contribute follow-up time (defined as a separate treatment episode) to digoxin (or statins) alone or the concomitant medications as appropriate, until they are right-censored at the first occurrence of: 1) the outcome, 2) the enrollment end of membership, and 3) the end of the observation period.

Given that digoxin (or statins) may be administered at a lower dose when used in combination with dronedarone than the use of digoxin (or statins) alone, and the drug interaction effect may be dose-related, the average daily dose of digoxin (or statins) will be adjusted for as a covariate in the analysis. It will be calculated as the total quantity prescribed divided by the total days supplied. If a statistically significant association of interaction is observed, further analysis will be performed to check dose-response relationship. For statins, the analyses will be conducted at equally effective doses which will address the effect of dose with the same cholesterol lowering effect. Based on published literature comparing statins efficacy, the following equally effective doses will be used in the secondary analysis for statins: atorvastatin 10mg, simvastatin 20mg, lovastatin 40mg, and pravastatin 40mg¹⁻².

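### The digitalis-intoxication model has no renal covariate, although the statin model has one, which leaves an avoidable risk of residual confounding in the digoxin hazard ratio

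*Protocol*

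**What the plan says.** Section 3.5 of the protocol builds each model from a common set plus additions for the particular outcome.

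- **Both outcomes:** "age at baseline, gender, cohort entry date, duration of AF/AFL, congestive heart failure (CHF) history, diabetes history, hypertension history, stroke history, myocardial infarction history", together with the dose of digoxin or statin.
- **Added for digitalis intoxication:** drugs with potent interactions, "including arbutamine, atazanavir, calcium chloride, calcium gluceptate, calcium gluconate, and saquinavir".
- **Added for rhabdomyolysis and myopathy:** a separate drug list, and then "History of renal failure (except for acute renal failure) will also be adjusted for the outcome of rhabdomyolysis and myopathy".

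The synopsis, under Covariates, draws the same line: "while for rhabdomyolysis and myopathy, chronic renal failure will also be adjusted for".

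Section 3.3 describes how average daily dose is obtained: "It will be calculated as the total quantity prescribed divided by the total days supplied". Section 3.2 has two exclusions, short enrolment and a recent diagnosis of the outcome. Neither concerns renal disease.

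**The concern.** Section 2 treats digitalis intoxication as a dose-related adverse event, so anything that raises digoxin exposure at a given dose bears on the outcome. Renal function is such a factor, because digoxin is cleared mainly by the kidney. The sponsor considered renal failure important enough to adjust for in the statin model and gives no reason for treating the digoxin model differently.

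The design offers no other protection. Section 3.1 states: "A retrospective cohort study is designed using information from a US claims database". Treatment is chosen in practice, and nothing in the protocol suggests that renal function is balanced across digoxin alone, digoxin with dronedarone and digoxin with amiodarone. If it is not, part of the difference in intoxication rates would reflect renal function and not the interaction.

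The digoxin contrast is one of the study's two questions. Under Section 3.7 a statistically significant association also decides whether the dose-response analysis is done, so a distorted estimate could start that step wrongly or prevent it. A larger cohort does not cure this kind of bias.

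**Working it through.** **Is the omission fixed by the protocol?** Yes. The synopsis and Section 3.5 agree, and both attach the renal term to the statin outcome by name. This is a stated choice of model, not a detail left for an analysis plan.

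**Do the other covariates stand in for renal function?** Only in part.

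- Age, heart failure, diabetes and hypertension are associated with renal function but do not measure it.
- Average daily dose is a dispensing measure. Two patients with the same dispensed dose and different renal function have different exposure.

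**How large could the effect be?** The protocol gives no figure for the prevalence of renal failure or its effect on intoxication, so there is no plan figure to reproduce. The event target in Section 5 and the hazard ratios in Table 3 do not depend on the covariate list. What follows is an illustration on assumed inputs.

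- p0 = prevalence of renal failure in digoxin-alone time (assumed)
- p1 = prevalence in concomitant time (assumed)
- RR = factor by which renal failure multiplies the risk of intoxication (assumed, 2 to 4)

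Factor applied to the hazard ratio when renal failure is left out:

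B = [1 + p1(RR − 1)] / [1 + p0(RR − 1)]

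This is a risk-ratio formula. It is a fair approximation for a hazard ratio here because the outcome is uncommon (Section 3.6 assumes 1.1%).

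| p0 | p1 | RR = 2 | RR = 3 | RR = 4 |
|---|---|---|---|---|
| 20% | 10% | 1.10/1.20 = 0.92 | 1.20/1.40 = 0.86 | 1.30/1.60 = 0.81 |
| 10% | 20% | 1.20/1.10 = 1.09 | 1.40/1.20 = 1.17 | 1.60/1.30 = 1.23 |
| 15% | 12% | 1.12/1.15 = 0.97 | 1.24/1.30 = 0.95 | 1.36/1.45 = 0.94 |
| equal | equal | 1.00 | 1.00 | 1.00 |

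For a true hazard ratio of 1.5:

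- 20% against 10%: 1.5 × 1.10/1.20 = 1.38, down to 1.5 × 1.30/1.60 = 1.22.
- 15% against 12%: 1.5 × 1.12/1.15 = 1.46, down to 1.5 × 1.36/1.45 = 1.41.

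With 10% against 20%, a true hazard ratio of 1.0 would read 1.09 to 1.23.

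For scale, Section 3.6 gives 1.42 as the hazard ratio for digitalis intoxication after five years of accrual. The wider gap moves a true 1.5 below that value. The narrower gap leaves it close to 1.42.

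**The case against.** The strongest reply is that no bias has been shown. Confounding needs renal failure to differ between the exposure groups after adjustment for the listed covariates, and the protocol has no data on that. The factors above are crude. Some of the imbalance would already be taken up by age, heart failure, diabetes, hypertension and dose, so the adjusted hazard ratio would probably be less affected. This stands, and it is why the point is a risk and not an error of known size.

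It is also fair to say that a baseline diagnosis code is a blunt measure of renal function. Section 3.1.1 reports that only 19% of members have any laboratory result, so adding the code would reduce the confounding but not remove it. That limits the benefit without being a reason to leave the term out.

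Three stronger readings are tempting, and the document does not support them.

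- **That the digoxin hazard ratio is confounded in a known direction.** The protocol gives no prevalence by exposure group, and the factor can fall on either side of 1.
- **That adjusting for dose without renal function makes matters worse.** It could, if dose had been lowered for renal impairment in this cohort. No section says so. The only reason Section 3.3 gives for a lower dose is co-use with dronedarone.
- **That the list of interacting drugs for digoxin is too short.** Section 3.5 states a rule, potent interactions only, and introduces the list with wording that need not be exhaustive. Whether other drugs meet the rule depends on a source outside the document.

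**Conclusion.** The point holds as a risk. The protocol twice confines the renal covariate to the statin outcome and gives no reason. The digitalis model has no renal term, and dispensed dose cannot replace one. The digoxin hazard ratios for dronedarone and for amiodarone are therefore open to residual confounding that could be reduced at little cost.

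The conclusion rests on one premise from outside the document, the renal clearance of digoxin, and on one condition the document cannot settle, that renal failure differs between the exposure groups. The size is unknown. The illustrated range of 0.81 to 1.23 rests on assumed crude prevalences and would shrink with a smaller gap or with effective adjustment by the partial proxies.

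**What to change.** In Section 3.5 and in the Covariates paragraph of the synopsis, replace the sentence that limits the renal term to one outcome with: *History of renal failure (except acute renal failure), defined at baseline in the same way in both cohorts, will be adjusted for in both outcome models.* Using the same term in both places also removes the small difference between the synopsis, which refers to chronic renal failure, and Section 3.5.

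The cost is modest. Section 3.2 sets up a separate cohort for each outcome, so the diagnosis codes, which Section 3.5 says are still to be provided, must be applied in the digoxin cohort as well as the statin cohort. No cohort size, event target or stated hazard ratio changes. The report should say that a yes/no diagnosis leaves some confounding by renal function in place.
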